#### 9.2. PHARAMCOKINETIC DATA

$C_{max}$  should occur at Day 7 ( $C_{Day 7}$ ), which will be listed and summarized as part of the concentration data. No additional presentations are required.

### 10. ANALYSIS OF PHARMACODYNAMICS

The PD parameters (CH50 and C3) will be evaluated using the PD population. Absolute values, changes from baseline and percentage changes from baseline for the PD parameters will be summarised by treatment group at each protocol specified time point using descriptive statistics.

For each PD parameter, the individual absolute values and individual changes from baseline will be presented graphically for each treatment group. Actual sampling times will be used for the graphical presentation of individual data.

The mean absolute values, mean changes from baseline and mean percentage changes from baseline will also be presented graphically by treatment group. Nominal sampling times will be used for the mean plots.

Individual PD parameters will be listed together with changes from baseline and percentage changes from baseline by treatment group.

## Statistical Analysis Plan

---

### **11. SAFETY**

All safety evaluation will be performed on the safety population.

#### **11.1. ADVERSE EVENTS**

AEs will be summarized separately for those occurred in the study eye, those in the fellow eye, and the non-ocular events.

AEs will be coded using the latest MedDRA version available.

According to the completion guidelines for this study any AE recorded prior to first dose of study drug should be recorded on the medical or ocular history page instead. So, all AEs recorded should be treatment emergent AEs (TEAE). However, a check will be made and AEs will be considered treatment-emergent unless there is clear indication that the event occurred prior to the first dose of study drug. AEs present prior to study drug administration that increased in severity or relationship to study drug after the first dose of study drug and up to 60 days beyond the last dose of study drug will be classed as TEAE. Events with missing or partial dates will be handled such that in the absence of contradictory information an AE is treatment emergent. So, for a missing start date (where stop date is after first dosing date or missing) the date will be imputed as the first dose date; for a missing stop date the date will be imputed as the last study date. If a partial date is recorded, the following convention will be used to assign the AE:

- If a start date is missing the day information and month/year is the same as first dose date then use first dose date, else '01' will be used for the day; if a start date is missing the month and the year is the same as first dose date then use first dose date, else January will be used for the start month.
- If a stop date is missing the day information and month/year is same as last study date then use last study date, else last day of the given month will be used for the stop day; if a stop date is missing the month and year is the same as last study date then use last study date, else December will be used for the stop month.

Only TEAEs will be included in the summary tables. An overall summary will present the number of subjects by treatment group and overall with:

- any TEAE
- any TEAE considered as related to study drug (evaluated by the investigator as Possibly Related or Probably Related or not reported)
- any serious TEAE
- any treatment emergent AESI (TEAESI) in either eye
- any TEAESI in study eye
- Maximum severity TEAE of none, mild, moderate, severe, life-threatening, death ; i.e. a subject with TEAEs at different intensities will be summarized at the most severe intensity

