8.3.4 Injection Visits – Monthly or EOM until month 12 -

Monthly Groups: Days 30, 60, 90, 120, 150, 180, 210, 240, 270, 300, 330 and 360 - Visits 4, 5, 6, 7, 8, 9, 10, 11, 12, 13, 14 and 15, respectively.

EOM Groups: Days 60, 120, 180, 240, 300 and 360 – Visits 4, 5, 6, 7, 8 and 9 respectively.

Unless specified, all ophthalmic procedures (including imaging) are to be performed on the **study eye only**. The following procedures will be performed at all injection visits:

1. Obtain information on any changes in medical health and/or the use of concomitant medications.
2. Collect vital signs pre- and post-dose. Vital signs will be measured within approximately 1 hour prior to dosing for the pre-dose time point. Post-dose vital signs readings will be performed within 30 minutes after dosing.
3. Collect blood for PK analysis.
4. Perform urine pregnancy test before APL-2 injection. **-WOCBP only-**
5. Perform BCVA. **-Both eyes on Day 360 only-**
6. Perform LL-BCVA. **-Both eyes on Day 360 only-**
7. Perform a complete ophthalmic exam including slit-lamp exam of the cornea, iris, anterior chamber, lens (LOCS III if any opacity on the lens noted) and aqueous reaction (cells and flare), dilated fundus exam of the vitreous and retina and IOP measurement.
8. Perform the IVT injection of APL-2 (or Sham injection) as described in the MOP.
9. Monitor the study eye within 15 minutes post-injection as outlined in [Section 9.8](#) and in the MOP.
10. Monitor for adverse events.

The following procedures will be performed only at specific visits, as noted:

1. Collect blood and urine for laboratory analysis and forward the samples to the central laboratory. - **Only on Days 60, 180 and 360 for all groups -**
2. Collect blood for genetic marker analysis (if applicable, see [Section 9.3](#)) and forward the samples to the central laboratory. - **Only on Days 60 for all groups -**
3. Perform SD-OCT imaging and forward the images to the CRC. - **Only on Days 60, 180 and 360 for all groups -**
4. Perform FAF imaging **of both eyes** and forward the images to the CRC. - **Only on Days 60, 180 and 360 for all groups -**
5. Perform IR imaging (if applicable) **of both eyes** and forward the images to the CRC. - **Only on Days 60, 180 and 360 for all groups -**

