11.4 Safety Assessment

Adverse events will be collected from the time of the first study drug administration until a subject completes the study or discontinues prematurely. A treatment-emergent adverse event is defined as any new adverse event reported or any worsening of an existing condition on or after the first dose of study drug. Treatment-emergent adverse events will be summarized by treatment group.

Adverse events will be summarized by MedDRA coding terms, and separate tabulations also will be produced for related adverse events (those considered by the PI as definitively drug related),

serious adverse events and discontinuations due to adverse events. Vital signs data and findings from physical and ophthalmologic examinations will be tabulated for changes over time on study. Laboratory parameters will be summarized for changes across study by using descriptive statistics.

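### SAP 11.1 stops counting worsening of pre-dose adverse events 60 days after the last dose; Protocol 11.4 sets no such limit, and SAP Section 13 does not declare the change

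*SAP*

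**What the plan says.** **Protocol 11.4** defines a treatment-emergent adverse event as "any new adverse event reported or any worsening of an existing condition on or after the first dose of study drug". New and worsened events are treated alike, and neither has an end date. The collection period is also stated: "Adverse events will be collected from the time of the first study drug administration until a subject completes the study or discontinues prematurely".

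**SAP 11.1** uses two rules.

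- General rule: "AEs will be considered treatment-emergent unless there is clear indication that the event occurred prior to the first dose of study drug". It has no end date.
- Rule for events already present before dosing: "AEs present prior to study drug administration that increased in severity or relationship to study drug after the first dose of study drug" count, but only "up to 60 days beyond the last dose of study drug will be classed as TEAE".

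The same section says that events before the first dose belong on the medical or ocular history page, so that every recorded AE should in principle be treatment-emergent; the two rules are applied as a check on that. It then states: "Only TEAEs will be included in the summary tables".

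SAP Section 2 gives the SAP precedence over the protocol on analysis. SAP Section 13 lists six changes from the protocol, including the renumbering of Day 0 as Day 1. The TEAE definition is not among them.

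**The concern.** The number and severity of TEAEs is the primary safety endpoint (Protocol 5.4, SAP 4.3.1). The SAP splits one protocol definition in two and puts an end date on only one half, without giving a reason or declaring the change. A late worsening on a record with a pre-dose onset would be a TEAE under the protocol and would be missing from the SAP's tables, while a new event on the same day would be counted. The limit is tied to the last dose, so it comes earliest for subjects who stop treatment and remain under observation.

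**Working it through.** The 60 days is a rule, so there is no computed figure to reproduce. The check sets the definitions side by side and then does the day arithmetic. Days use the protocol's numbering (first dose = Day 0); SAP study days are one higher.

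**1. Definitions**

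| Event | Protocol 11.4 | SAP 11.1 |
|---|---|---|
| New AE | first dose onward, no end | first dose onward, no end |
| Worsening of a pre-dose event | first dose onward, no end | first dose to last dose + 60 days |

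The documents differ in the second row only.

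**2. Inputs**

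- Last scheduled injection: Day 360 ± 6 in all four arms (Protocol 8.3.4 and Section 2 flow charts). For the monthly arms the schedule reads "Monthly Groups: Days 30, 60, 90, 120, 150, 180, 210, 240, 270, 300, 330 and 360".
- Month 15 visit: Day 450 ± 14. Month 18 visit: Day 540 ± 14 (flow charts).
- Limit: 60 days after the last dose (SAP 11.1).

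**3. Cutoff for subjects who complete treatment** (cutoff = day of last injection + 60)

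- Nominal: 360 + 60 = Day 420.
- Earliest and latest in-window injection: 354 + 60 = Day 414; 366 + 60 = Day 426.

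**4. Against the follow-up visits**

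- Earliest in-window Month 15 visit: 450 − 14 = Day 436, which is 436 − 426 = 10 to 436 − 414 = 22 days after the cutoff.
- Smallest gap from injection to visit: 436 − 366 = 70 days, more than 60.
- Earliest in-window Month 18 visit: 540 − 14 = Day 526, also past the cutoff.

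**5. Share of follow-up**

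- Follow-up: 540 − 360 = 180 days.
- Inside the limit: 60/180 = 33%. Outside: 120/180 = 67%.

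**6. Subjects who stop treatment but stay in the study** (allowed by Protocol 8.1 and 10.5.1)

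| Last dose | Cutoff | Days beyond cutoff, to Day 360 | Days beyond cutoff, to Day 540 |
|---|---|---|---|
| Day 60 | 120 | 240 | 420 |
| Day 120 | 180 | 180 | 360 |
| Day 180 | 240 | 120 | 300 |
| Day 240 | 300 | 60 | 240 |
| Day 300 | 360 | 0 | 180 |

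A last dose on Day 300 or later therefore puts the cutoff at or after Day 360.

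The cutoff can also differ by schedule. If only the Month 12 injection is missed, it is 330 + 60 = Day 390 in a monthly arm and 300 + 60 = Day 360 in an every-other-month arm.

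**7. Which report is affected**

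SAP Section 2 puts data to Month 12 in the CSR and the remaining follow-up in an addendum. By step 6, the limit can act on data to Month 12 only for subjects who stopped early. It acts on later data for anyone followed past the cutoff. Those later data go mainly to the addendum, although SAP Sections 2 and 12 let some post-Month 12 safety data, notably SAEs and AESI, into the CSR.

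**The case against.** The strongest reply is that the rule has little to act on. SAP 11.1 sends pre-dose conditions to the history pages and presumes that every AE record is treatment-emergent. If a site enters the worsening of a history-page condition as an AE with a post-dose start, the general rule applies and there is no cutoff. The limit reaches only AE records that carry a pre-dose onset despite the guideline. Missing or partial dates are also resolved towards inclusion. This stands. The affected set is probably small and could be empty, although the documents do not say how sites enter worsening.

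A reader might infer from steps 4 and 5 that both follow-up visits, or two thirds of follow-up, drop out of the TEAE tables. The documents do not support that. New events have no limit. For worsened events the limit concerns the date of the worsening, so one dated by Day 420 and first reported at Month 15 still counts. The SAP's Month 15 analysis window also opens at Study Day 412, before the nominal cutoff of Study Day 421, so an early visit outside the protocol window could fall within the 60 days. The 120 days and the 70-day gap measure calendar time, not lost events.

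Three further points can be made for the plan.

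- A bounded post-dose period is a recognised way to define treatment emergence. That could justify a limit, but it does not explain one that applies to worsened events and not to new ones.
- The SAP takes precedence over the protocol. That settles which text governs; it does not declare or explain the departure.
- The data stay visible. SAP 6.1 commits to listing all data, and SAP 11.1 adds separate listings of serious AEs, AESI and AEs leading to discontinuation. What is lost is tabulation, not the record.

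**Conclusion.** The point holds as an undeclared inconsistency in the definition behind the primary safety endpoint, with a minor consequence. For AE records with a pre-dose onset, an increase in severity or relationship dated after the cutoff is left out of the TEAE summary tables. The cutoff is Day 420 after a Day 360 last dose (414 to 426 across the injection window) and earlier for those who stop treatment and stay in the study. The main effect is on the 18-month addendum.

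This rests on two assumptions: that some AE records carry a pre-dose onset, and that the date of worsening can be read from them. The number of affected events cannot be derived from the documents.

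A reader might also infer that the rule favours one arm, or that the safety comparison is biased. The documents give no basis for a direction or a size: the limit is the same number of days in every arm, and any imbalance would depend on treatment discontinuation and recording practice that are not known in advance.

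**What to change.** In SAP 11.1, delete the 60-day limit from the sentence on events present before dosing, so that worsening counts whenever it occurs after the first dose. New and worsened events then have the same open end, as in Protocol 11.4, and for a Day 360 last dose the window for worsening runs 180 days instead of 60. No entry in Section 13 is then needed for the limit.

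If the sponsor prefers to keep a limit, Protocol 11.4 and SAP 11.1 still have to be reconciled: the change should be listed in Section 13 with a reason, including why it applies to worsened events alone.

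The cost is one sentence and possibly slightly higher TEAE counts, some of them from off-treatment time. Separate on-treatment and post-treatment tables would help a reader tell these apart, but they are optional, add output and are not needed for the fix.

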## Statistical Analysis Plan

---

- any TEAE leading to study drug discontinuation
- any TEAE leading to death

The table will also include the total number of TEAEs reported and total number of TEAESI reported. The total number of unique terms within subjects will also be presented, counting each TEAE only once within each subject.

The number and percentage of subjects with TEAEs will be presented by SOC, PT and by treatment group and overall. Subjects with multiple TEAEs within a SOC or SOC/PT combination will be counted only once for that SOC or SOC/PT combination. Similar summaries will be presented for related TEAEs, TEAEs leading to discontinuation, serious TEAEs and TEAESI in study eye.

Summaries of TEAEs by maximum severity (mild, moderate, severe, Life-threatening or death) will be presented. This will be repeated for TEAESI in study eye.

All summaries will be ordered by descending order of total events in the APL-2 pooled group.

All TEAEs will be listed by treatment group, subject and AE onset date. Separate listings of serious AEs, AESI and AEs leading to discontinuation of study drug will also be generated. For the listing of AESI the effected eye (study or fellow) will also be listed.

### **11.2. INTRA OCULAR PRESSURE (IOP)**

The observed and change from baseline values in IOP over time will be summarized by treatment group and protocol specified time points for the safety population. Summaries will present the descriptive statistics for baseline and change from baseline data. The acute change in IOP after each injection (i.e., change from pre-injection to post-injection value) will also be summarized at each protocol specified time point.

The number of subjects with IOP  $\geq 30$  mmHg post injection will be summarized by treatment group, visit and over the whole study.

### **11.3. ANTERIOR SEGMENT EXAMINATION**

Anterior segment examination endpoints (abnormal reaction to light, active inflammation present in cornea, abnormal anterior chamber, any opacity in lens, aqueous reaction flare and aqueous reaction cells) will be summarized separately for the study eye and the fellow eye by treatment group and protocol specified time points for the MITT population, using summary statistics for categorical variables.

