### **RATIONALE AND SUMMARY OF REVISION V2.0:**

The Statistical Analysis Plan (SAP) is revised for the following reasons:

- To specify that the CSR will be based on the primary 12-month data cut. An addendum to the CSR will be generated with the final 18-month data;
- To move anterior and posterior segment examinations from efficacy sections to safety sections;
- To add a subgroup analysis of the primary endpoint by GA lesion size at baseline;
- To remove redundant summary tables;
- To change the comparison method from chi-squared test to Fisher's exact test for incidence of macular neovascularization to handle the situation of low incidence in any group;
- To specify that adverse events will be summarized separately for those occurs in the study eyes, in the fellow eye, and those that are non-ocular;
- To add the summaries for prior/concomitant medications used in the study eyes, and for those used in the fellow eyes;
- To modify the numbering and titles of the planned summary tables, listings and figures (TLFs) to match those specified in the TLF Shells documents; and
- Additional editorial changes across the document to improve clarity.

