### **4.3.3. Anterior Segment Examination**

The anterior segment examination data is collected on the slit lamp examination eCRF page. The anterior segment examination is performed throughout the study for the study eye and at screening and end of study only for the fellow eye. The following endpoints will be investigated for the study eye and fellow eye (screening and end of study only):

- Abnormal reaction to light
- Active inflammation present in cornea
- Abnormal anterior chamber
- Any opacity in lens. Note if response to lens question is missing but anterior chamber response is normal then response will be defined as no opacity in the lens.
- Aqueous reaction - flare (0, trace, 1+, 2-3+, 4+). Note if response to aqueous reaction flare question is missing but anterior chamber response is normal then response will be defined as 0.
- Aqueous reaction - cells (0, trace, 1+, 2+, 3+, 4+). Note if response to aqueous reaction cells question is missing but anterior chamber response is normal then response will be defined as 0.

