### **4.3.4. Posterior Segment Examination**

The posterior segment examination data is collected on the dilated binocular indirect ophthalmoscopy eCRF page. The posterior segment examination is performed throughout the study for the study eye and at screening and end of study only for the fellow eye. The following endpoints will be investigated for the study eye and fellow eye (screening and end of study only):

- Posterior segment abnormalities (none, mild, moderate, severe)
- Presence of posterior vitreous detachment
- Presence of retinal haemorrhage/detachment
- Vitreal haemorrhage density (none, 1+, 2+, 3+, 4+)
- Vitreous cells evaluation (none, 1+, 2+, 3+, 4+)

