### **5.3. SAFETY POPULATION**

The safety population will include all subjects randomized who receive at least one injection of study medication. The safety population summary groups will be based on the actual treatment received for the whole duration of the study. The grouping rule for subjects who receive study medication from the incorrect injection during the study will be decided on a case by case basis before database lock. This population will be used for all safety analyses.

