## Statistical Analysis Plan

---

treatment group and protocol specified time points for the MITT population, using summary statistics for categorical variables.

All other ophthalmology data collected based on Slit Lamp and Dilated Binocular Indirect Ophthalmoscopy examinations but not discussed in other sections of the SAP will be listed by treatment group.

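### SAP 11.3 and 11.4 assign the anterior- and posterior-segment safety examinations to the MITT population, against the safety-population rule in SAP 5.3 and SAP 11

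*SAP*

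**What the plan says.** The general rule appears twice in the SAP, with no exception either time. SAP 5.3 says of the safety population: "This population will be used for all safety analyses". SAP 11 opens with: "All safety evaluation will be performed on the safety population". That population is everyone randomized who had at least one injection, grouped by treatment actually received. Protocol 11.1.3 defines the safety set in the same way.

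The anterior and posterior segment examinations sit under the Safety Endpoints heading (SAP 4.3.3 and 4.3.4) and are analysed within Section 11. Yet SAP 11.3 summarizes the first "by treatment group and protocol specified time points for the MITT population", and SAP 11.4 summarizes the second by "treatment group and protocol specified time points for the MITT population, using summary statistics for categorical variables".

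SAP 5.5 restricts MITT to injected subjects who have lesion data from a visit at Month 2 or later, keeps them in their randomized group, and assigns the set to efficacy and exploratory endpoints. It does not mention safety. The neighbouring ocular safety endpoint, IOP in SAP 11.2, is summarized at "protocol specified time points for the safety population".

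**The concern.** The text gives a programmer two incompatible instructions for the same tables. If 11.3 and 11.4 are followed, two things change relative to the safety rule.

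- **Membership.** A subject who is injected, examined at Day 7 and then leaves without lesion data from Month 2 onward drops out of the by-visit tables of flare, cells, vitreous cells, vitreous hemorrhage density and retinal findings. The same subject stays in the IOP table.
- **Grouping.** Subjects are counted by assigned treatment instead of treatment received. This matters only if someone is given the wrong treatment.

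The protocol synopsis names ocular inflammation, vitreous hemorrhage and retinal detachment or tear as secondary safety endpoints, and the Day 7 visit is there to check acute safety after the first injection. If an ocular problem is why a subject leaves early, the omission is not random. What these tables would lack is the by-visit grade, or a finding that the investigator did not report as an adverse event.

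**Working it through.** **Comparing the sections**

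| Place in SAP | Subject matter | Population | Grouping |
|---|---|---|---|
| 5.3 | every safety analysis | Safety | as treated |
| 11, opening | every safety evaluation | Safety | as treated |
| 5.5 | efficacy and exploratory | MITT | as randomized |
| 11.2 | IOP | Safety | as treated |
| 11.3 | anterior segment | MITT | as randomized |
| 11.4 | posterior segment | MITT | as randomized |

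SAP 13, which lists departures from the protocol, does not list this one. The V2.0 revision summary gives one of its purposes as: "To move anterior and posterior segment examinations from efficacy sections to safety sections". The likeliest explanation is that the population wording travelled with the text. That is an inference. The revision summary is not itself in error; the inconsistency lies in the current 11.3 and 11.4.

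**How many subjects could be affected**

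The plan states no figure for early loss, so there is nothing to reproduce, and what follows is an illustration.

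Inputs: 240 randomized and 15-20% loss to follow-up (SAP 3.3); Month 2 analysis window opening at Day 47, with target Day 61 (SAP 6.3, Table 2); first dose on Day 1. The cut-offs are therefore 46 and 60 days after first dose. Assumption: no termination image counts toward MITT.

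*Even loss*, N = 240 × loss × days / duration. The low end spreads 15% over 540 days, the high end 20% over 360 days.

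- Before Day 47: 240 × 0.15 × 46/540 = 3.1; 240 × 0.20 × 46/360 = 6.1.
- Before Day 61: 240 × 0.15 × 60/540 = 4.0; 240 × 0.20 × 60/360 = 8.0.

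*Constant rate over 12 months*, N = 240 × [1 − (1 − loss)^(days/360)].

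- Before Day 47: 240 × (1 − 0.85^(46/360)) = 240 × 0.0206 = 4.9; 240 × (1 − 0.80^(46/360)) = 240 × 0.0281 = 6.7.
- Before Day 61: 240 × (1 − 0.85^(60/360)) = 240 × 0.0267 = 6.4; 240 × (1 − 0.80^(60/360)) = 240 × 0.0365 = 8.8.

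Taken together, this is about 3 to 9 of 240, or 1 to 3 in an arm of 80. The affected post-dose scheduled visits are Day 7 in all arms and Month 1 in the monthly arms only, since the every-other-month arms have no Month 1 visit. One omitted positive finding in an arm of 80 shifts a percentage by at most 1/80 = 1.25 points.

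**The case against.** **A specific instruction overrides a general one.** This would carry weight if the general rule were a default. It is instead stated twice without qualification, SAP 5.5 gives MITT a scope that excludes safety, and no exception is recorded in SAP 13. The argument does not make the text consistent.

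**Little would be missing from the report.** This largely stands. Adverse events of any grade and AESIs are summarized on the safety population, SAP 4.3.1 provides for a clinical review of all ocular adverse events before lock so that no AESI is missed, and SAP 6.1 has all data listed. A reader might infer that ocular safety events would disappear from the study report. The documents do not support that: what is at risk is a row in a descriptive by-visit table, and no hypothesis test is involved.

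**The number affected may be near zero.** Also fair. Subjects who withdraw before Month 12 should have a termination visit, which includes FAF, and Table 2 treats the end-of-study visit as the final assessment, so some early leavers may remain in MITT. Under SAP 5.5, only ITT is used if MITT and ITT coincide, and ITT has the same membership rule as the safety population. But that rule depends on the data, leaves a choice when differences are minimal, never mentions the safety population, and would still group subjects as randomized.

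**The change comes late.** SAP V3.0 was written after the 12-month results had been reviewed (SAP 4.1, 8.1.3). A change of population now could make the 18-month tables disagree with 12-month tables already produced. This affects the cost, not the finding.

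A reader might also infer a clash of denominators between lens opacity in 11.3 and the LOCS III summary in 11.5. That does not follow: 11.5 reports scores on its own stated subset of phakic subjects with a LOCS III assessment, and that subset would still differ from the 11.3 population after the correction.

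**Conclusion.** The contradiction is real and can be established from the text alone. SAP 11.3 and 11.4 name a population that SAP 5.3, the opening of SAP 11 and the scope given in SAP 5.5 all rule out for safety endpoints. It is a wrong stated rule, not missing detail.

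It is a minor point. The effect is limited to descriptive by-visit tables. The range of about 3 to 9 of 240 rests on the planned 15-20% loss being spread evenly or at a constant rate, and on no termination image counting toward MITT. Neither assumption comes from the documents, and the true number may be close to zero. The grouping difference matters only if treatment is misallocated. The SAP's index of tables was not in the text examined, so the population named in the table titles could not be checked.

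**What to change.** In SAP 11.3 and 11.4, replace MITT with the safety population, grouped by treatment received, as SAP 11.2 already does. Align the titles of the matching tables and the population flag in their programs.

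The cost is two phrases and a flag, with no new data. If the 12-month tables were already produced on MITT, either rerun them or document the change in the CSR addendum, so that the 12- and 18-month outputs can be compared.

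This correction covers only 11.3 and 11.4. Whether the sets used elsewhere suit their purpose, for example MITT for neovascularization events in SAP 8.2.2 or ITT and MITT for exposure in SAP 7.6, is a separate question not settled here.
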